13.3.2. Duration of Response

Duration of response, defined as the time from first documented evidence of CR or PR until disease progression or death due to any cause among patients who achieve an overall response (i.e., unconfirmed or confirmed CR or PR) will be summarized.

Censoring rules will follow those of the PFS analysis defined in Section 13.3.1.

If sample size permits, the median duration of response will be calculated from the Kaplan-Meier estimates. First and third quartiles will also be calculated along with associated 95% confidence intervals if there are a sufficient number of responders who subsequently progress or die due to any cause. A figure and listing of duration of response will be provided.

14. PHARMACOKINETIC ANALYSES

The reconciliation of the PK Case Report Form (CRF) and SMS2000 data will be performed by, or under the direct auspices of, Data Sciences - Oncology, GlaxoSmithKline.

The merge of PK concentration data, randomisation, and CRF data to generate a dataset with actual blood sampling times, actual time relative to dosing, and PK concentrations will be performed after DBF by, or under the direct auspices of, Oncology Quantitative Sciences (Programmer), GlaxoSmithKline.

Unless otherwise stated, all tables, figures and listings in this section will be based on the Biomarker population as defined in Section 6, and all summaries, figures and data listings will use treatment labels as specified in Section 7.

The lists of displays for PK, including population to use for each display, are shown in Section 18.1.4 of the RAP.

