- 22. Biopsies are to be taken at the judgement of the investigator at the various time-points to ensure that any potential risk or impact to the patients are kept to a minimum, All biopsies, be they from cutaneous or sub-cutaneous lesions, are to be performed only if the lesions are easily accessible. Biopsies are to be performed by either the investigator, a dermatologist, a surgeon or a physician qualified in radiology if an ultrasound-led biopsy is necessary.
- 23. For Subjects enrolled in France, refer to the Appendix 6: Additional Monitoring for Patients Enrolled in France

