#### 7.5. Pharmacokinetics

As part of the secondary objectives of this study, concentrations of trametinib and of dabrafenib and its metabolites (GSK2285403, GSK2298683, and GSK2167542) will be determined at each time point during treatment when the skin and tumour biopsies are performed. During the monotherapy treatment in arm A and B, only trametinib or dabarafenib and its metabolites will be measured. During combination, both drugs and metabolites will be measured.

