#### 7.5.1. Blood Sample Collection for Pharmacokinetics

Blood samples for PK analyses of dabrafenib, trametinib, and metabolites of dabrafenib will be collected at the same day as the tumour and skin biopsies are performed during treatment (Week 2, 8 and 10). Patients with morning clinic visits will be instructed to withhold their morning dose, and samples will be collected prior to dabrafenib and trametinib administration; for patients with afternoon clinic visits, patients will take their morning doses as usual, and samples will be collected 4-8 hours following dabrafenib and trametinib administration. Date and exact time of pharmacokinetic sample and of most recent dose will be recorded. No more than 25 mL of blood will be collected over the duration of the study for PK blood sample collection, including any extra assessments that may be required.

Details of PK blood sample collection (including volume to be collected), processing, storage, and shipping procedures will be provided in the SPM.

2012N132406\_01 **CONFIDENTIAL**BRF116613

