6. ANALYSIS POPULATIONS

The **Intent-to-Treat Population (ITT)** will consist of all randomized patients whether or not randomized treatment was administered. This population will be based on the treatment to which the patient was randomized and will be the primary population for the analysis of efficacy data. Any patient who receives a treatment randomization number will be considered to have been randomized.

The **Safety Population** will consist of all patients who received at least one dose of randomized treatment and will be based on the actual treatment received. This population will be used for the analysis of clinical safety data.

The **Biomarker Population** will consist of all patients with biopsy performed at screening and at least once during treatment.

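### Every planned PK display is limited to patients with a biopsy pair, so dosed patients with valid concentrations but no pair are left out, even from the listings

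*SAP*

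**What the plan says.** SAP Section 14 sets a default for the PK section: unless something else is stated, "all tables, figures and listings in this section will be based on the Biomarker population as defined in Section 6". It then defers to the display list: "The lists of displays for PK, including population to use for each display, are shown in Section 18.1.4 of the RAP". In that list the population column reads Biomarker for every PK display.

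SAP Section 6 (and Protocol Section 9.3.1, in the same terms) defines the Biomarker Population as "all patients with biopsy performed at screening and at least once during treatment". The Safety Population, by contrast, "will consist of all patients who received at least one dose of randomized treatment and will be based on the actual treatment received". No PK population is defined, and Protocol Section 9.3.2 assigns analysis sets to efficacy, safety and biomarkers but none to PK.

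On sampling, Protocol Section 7.5 says that concentrations will be "determined at each time point during treatment when the skin and tumour biopsies are performed", and Section 7.5.1 places routine samples on the biopsy days at Weeks 2, 8 and 10. Table 19 gives PK blood its own row at those weeks and at progression. Footnote 22 to that table makes biopsies discretionary: "Biopsies are to be taken at the judgement of the investigator at the various time-points", and only where the lesion is easily accessible. That footnote is attached to the two biopsy rows and not to the PK row.

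**The concern.** The set chosen for PK is defined by tissue, while PK data come from blood. The SAP's secondary objective relates exposure to clinical response and to toxicity. Response is analysed in the ITT population (SAP Section 13) and toxicity in the Safety Population (SAP Section 12). Only the link between exposure and p-ERK needs a biopsy.

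If the rule is followed as written, some dosed patients with usable concentrations are absent from the PK summaries and plots, and also from the listings, where a reader would look for all the data. The PK set then also fails to match the two sets with which exposure is to be compared.

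**Working it through.** **Step 1: is there any exception to the default?** Count the entries in SAP Section 18.1.4:

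- Tables 4.0010 to 4.0014: 5, all Biomarker.
- Figures 14.0010 to 14.0014, 14.0020 to 14.0024 and 14.2010 to 14.2014: 15, all Biomarker.
- Listings 24.1010 to 24.1014: 5, all Biomarker.

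The total is 5 + 15 + 5 = 25 displays, with no exception.

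**Step 2: who is excluded?** Apply the Section 6 definition to a dosed patient with at least one valid concentration:

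| Baseline biopsy | On-treatment biopsies | In PK displays? |
|---|---|---|
| Yes | One or more | Yes |
| Yes | None | No |
| No | Any number | No |

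Missing one or two of the Week 2, 8 and 10 biopsies excludes nobody. The definition does not say tumour biopsy, and Table 19 schedules skin biopsies at the same visits, so a patient with paired skin samples alone could qualify.

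**Step 3: can concentrations exist without a biopsy pair?** Yes. The PK row of Table 19 stands apart from the biopsy rows and does not carry the discretion footnote. Section 7.2 also expects some missing biopsies, since it allows extra recruitment to secure enough patients with the key ones. But Sections 7.5 and 7.5.1 tie routine PK to biopsy days, so PK without a biopsy is possible rather than typical.

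**Step 4: compare with the SAP's own listing rules.** Section 9.3 puts data from all assessments into listings. Section 14.1 keeps even concentrations that were excluded from PK parameter derivation in the listings, flagged with an asterisk. Leaving out a valid concentration because a biopsy is missing is stricter than that.

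**Step 5: how many patients?** The plan gives no figure for PK. Its only precision figure concerns p-ERK (SAP Section 5.1) and reproduces: t(0.975, 14) × 30 / √15 = 2.145 × 30 / 3.873 = 16.61. It is unaffected by this point, but it shows a design that enrols 54 / 3 = 18 per arm and counts on 15. If all 18 gave PK and only 15 were in the Biomarker Population, 3 × (18 − 15) = 9 of 54 patients (16.7%) would be omitted.

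The documents give no rate of dosed patients without a pair, so the range below is an assumption. With a proportion m lacking a pair, the number kept per arm is 18 × (1 − m), rounded to a whole patient.

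| Assumed m | Kept per arm | Omitted of 54 |
|---|---|---|
| 10% | 16 | 54 − 48 = 6 |
| 20% | 14 | 54 − 42 = 12 |
| 30% | 13 | 54 − 39 = 15 |
| 40% | 11 | 54 − 33 = 21 |
| 50% | 9 | 54 − 27 = 27 |

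These counts are upper bounds, because some patients without a pair will have no PK sample either.

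**The case against.** The strongest defence is that the affected group is small. Routine PK is drawn on biopsy days, accessible tumours are an inclusion criterion, refusal of tumour and skin biopsies is an exclusion criterion, and one on-treatment biopsy is enough to qualify. The PK displays are also descriptive: Section 14.1 plans means, standard deviations, medians and ranges, with no interval or test. The analyses that relate exposure to outcome sit elsewhere, in population PK (Section 14.2) and PK/PD (Section 15), each under a separate plan. All of this stands, and it limits the size of the point. It does not supply a reason to require a biopsy before a plasma concentration is listed. The separate analyses are no full remedy either, since both are to be done only if the data warrant and neither section states its population.

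Four stronger readings are tempting and are not supported:

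- *The 20% allowance in Section 5.1 (0.20 × 54 = 10.8 patients) measures the loss.* It is an allowance for early dropout. A patient who leaves before Week 2 has no scheduled PK sample to lose.
- *The concentrations are discarded.* They are left out of the planned PK displays, but may still be used in the population PK or PK/PD work.
- *The PK summaries are biased with respect to response or toxicity.* That is plausible if missing biopsies reflect lesion accessibility or tolerance, but nothing in the documents establishes the link.
- *Almost nobody qualifies, because the definition says screening while Table 19 and SAP Section 9.2.7 place the baseline biopsy on Day 1.* The baseline biopsy is the sensible reading. The wording needs aligning, but that is a separate matter.

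**Conclusion.** The point holds as a gap in completeness that can be closed at almost no cost. As written, the SAP omits from all 25 PK displays any dosed patient with valid concentrations who lacks a baseline biopsy or has no on-treatment biopsy at all. That conclusion follows from the definitions and the display list and needs no assumption.

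The size is not known. The figure of 6 to 27 of 54 rests on an assumed 10% to 50% without a pair, and on every such patient having PK data, which makes it an upper bound. The true number may be small. Harm to the exposure objective is not shown. What is shown is a PK set that does not match the ITT and Safety sets used for response and toxicity.

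**What to change.** Add a PK Population to SAP Section 6: all patients who received at least one dose of study treatment and have at least one evaluable post-dose concentration, grouped by actual treatment. Name it in Section 14 and in the population column for Tables 4.0010 to 4.0014, all 14.x figures and Listings 24.1010 to 24.1014. Keep the Biomarker Population for exposure versus p-ERK only.

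Two small additions help. Ask that the separate population PK and PK/PD plans state their populations. Say also where the samples taken at progression or prompted by visual changes, liver events or overdose will be listed: the current PK displays are specified for Weeks 2, 8 and 10, so a new population flag alone would not bring those samples in.

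The cost is one population flag and a text change in the SAP. No new data are needed, and the p-ERK sample size is untouched.

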14.1. Drug Concentration Measures

Concentrations of GSK1120212 and GSK2118436 and its metabolites (GSK2284503, GSK2298683, and GSK2167542) will be listed and summarised by treatment group and nominal time. Standard summary statistics will be calculated (i.e. mean, standard deviation, median, minimum and maximum). Refer to the PK Guidance document [GUI_51487](#), “Non-Compartmental Analysis of Pharmacokinetic Data”, for more information regarding the handling of concentrations below the assay’s lower limit of quantification (NQ).

Individual concentration-time profiles and median/mean profiles by treatment group will be plotted using actual elapsed time for individual plots and nominal time for median/mean profiles. Each of the figures will contain one plot on the untransformed scale (i.e. a linear plot) and one plot on the log transformed scale (i.e. log-linear plot). See Pharmacokinetic Source Figures and Tables for details.

Any concentration data excluded from the derivation of PK parameters by Clinical Pharmacology Modelling and Simulation (CPMS) should be omitted from any figures and summaries, and flagged with an asterisk in the relevant data listings, with a footnote to indicate that these values have been omitted from subsequent analyses.

14.2. Population Pharmacokinetic Analyses

If data warrant, pharmacokinetic data will be analyzed using a population approach. A nonlinear mixed effects model will be used to determine population pharmacokinetic

parameters such as CL/F (apparent clearance following oral dosing) and other parameters as data permit and identify relevant covariates (e.g., age, weight, or disease related covariates) that explain variability. Concentration data will be pooled with data from other studies. Details on the population analysis will be the focus of a separate analysis plan and will be the responsibility of CPMS.

15. PHARMACOKINETIC/PHARMACODYNAMIC ANALYSES

If data warrant, exploratory analyses will be performed to examine the relationship between plasma concentration of dabrafenib and/or trametinib and pharmacodynamic endpoints such as tumor size, biomarker changes and other clinical and safety measures.

Initially, the relationships will be explored graphically. If these exploratory graphical analyses suggest a relationship between pharmacodynamic endpoints and concentration or pharmacokinetic parameters, PK/PD models may be derived and evaluated. Additional exploratory analyses may be performed to further characterize biomarkers.

Further details of PK/PD analyses will be described under a separate RAP. Results of the PK/PD analyses may be included in a report separate from the clinical study report.

16. BIOMARKER ANALYSES

The results of translational research investigations not related to the H-Score of p-ERK will be reported separately from the main clinical study report. All endpoints of interest from all comparisons will be descriptively and/or graphically summarized as appropriate to the data. Further details on the translational research analyses will be described under a separate RAP.

18. ATTACHMENTS

18.1. Table of Contents for Data Display Specifications

The following flexible system will be used to number the listings, tables and figures:

- Study Population:
 - tables, 1.xxxx
 - ICH-listings, 21.xxxx
 - Other-listings, 30.xxxx (30.0010 – 30.0110)
- Efficacy:
 - tables, 2.xxxx;
 - figures, 12.xxxx;
 - ICH-listings, 22.xxxx
- Safety:
 - tables, 3.xxxx;
 - figures, 13.xxxx;
 - ICH-listings, 23.xxxx
 - Other-listings, 30.xxxx (30.0240 – 30.0330)
- Pharmacokinetic:
 - tables, 4.xxxx;
 - figures, 14.xxxx;
 - ICH-listings, 24.xxxx
- Biomarker:
 - tables, 5.xxxx;
 - figures, 15.xxxx
 - Listings, 25.xxxx

Note: please specify which value will be used as baseline in the listing for lab, ECG, and vital sign.

Listed below are the planned figures, tables and listings to be produced for inclusion in clinical study report

18.1.1. Study Population (Section 1)**18.1.1.1. Tables**

Table No.	Title	Population	Component / Therapeutic Area (hyperlinked to IDSL LN DB)	IDSL No. or Example Shell No.	Study-Specific Display Notes	Deliverable Priority
1.0010	Summary of Study Populations	ITT	Subject Accountability/Oncology	POP1	Percentages for each cell are based on 'N' at the top of each column.	SAC
1.1010	Summary of Number of Subjects by Centre	ITT	Enrollment/Core	NS1		SAC
1.1110	Summary of Subject Disposition	ITT	Disposition/Core	ES8		SAC
1.1220	Summary of Study Treatment Status	ITT	Investigational Product Discontinuation/Core	SD4	Reasons for discontinuation will be presented in the order they are displayed on the eCRF. Only include 'Missing' rows where applicable.	SAC
1.1310	Summary of Inclusion/Exclusion Criteria Deviations	ITT	Inclusion & Exclusion Criteria/Core	IE1		SAC
1.1410	Summary of Protocol Deviations	ITT	Protocol Deviations/Core	DV1A		SAC
1.2010	Summary of Demographic Characteristics	ITT	Demography/Core	DM1		SAC
1.2011	Age Group Breakdown for the Trial	ITT			See Mock-Up. Based on new EMA requirements. Use combined data from all three arms.	SAC
1.2020	Summary of Race and Racial Combinations	ITT	Demography/Core	DM5		SAC
1.2110	Summary of Disease Burden at Baseline	ITT	Lesion Assessments/Oncology	LA1		SAC
1.2120	Summary of Substance Use	ITT	Substance Use/Core	SU1		SAC
1.3110	Summary of Cancer Related Medical Conditions at Screening	ITT	Medical Conditions/Core	MH1		SAC
1.3112	Summary of Non-Cancer-Related Medical Conditions at Screening	ITT	Medical Conditions/Core	MH1		SAC

CONFIDENTIAL

BRF116613

Table No.	Title	Population	Component / Therapeutic Area (hyperlinked to IDSL LN DB)	IDSL No. or Example Shell No.	Study-Specific Display Notes	Deliverable Priority
1.3210	Summary of Disease Characteristics at Initial Diagnosis	ITT	Disease Characteristics/Oncology	DC1	Sections include: Time since initial diagnosis (weeks), and Primary Tumour Type	SAC
1.3220	Summary of Disease Characteristics at Screening	ITT	Disease Characteristics/Oncology	DC2	Sections include: Measurable disease at baseline, Presence of non-target lesions at baseline, and Stage	SAC
1.3230	Summary of Metastatic Disease at Screening	ITT	Metastatic Disease/Oncology	MD1		SAC
1.4010	Summary of Prior Anti-Cancer Therapy	ITT	Anti-Cancer Therapy/Oncology	AC2		SAC
1.4020	Summary of Prior Dictionary Coded Anti-Cancer Therapy	ITT	Concomitant Medication/Core	CM1		SAC
1.4030	Summary of Number of Prior Anti-Cancer Therapy Regimens	ITT	Anti-Cancer Therapy/Oncology	AC3	Therapies should be sorted in highest to lowest incidence. Total column is required.	SAC
1.4040	Summary of Best Response to Most Recent Prior Anti-Cancer Therapy	ITT	Anti-Cancer Therapy/Oncology	AC4		SAC
1.4110	Summary of Prior Cancer-Related Surgical Procedures	ITT	Surgical-Medical Procedures/Oncology	OSP1		SAC
1.4110	Summary of Prior Non-Cancer Related Surgical Procedures	ITT	Surgical-Medical Procedures/Oncology	OSP1		SAC
1.5010	Summary of Concomitant Medications by Ingredient	ITT	Concomitant Medications/Core	CM8	Medications will be sorted in descending order of total incidence across treatment groups for the ATC level 1 (CM1 only) and in descending order of total incidence of ingredient within ATC level (CM1) or overall (CM8). In case of a tie, sort tied ingredients alphabetically.	SAC
1.5011	Summary of Blood or Blood Supportive Care Products while On-Therapy	ITT	Concomitant Medications/Core	CM8	Medications will be sorted in descending order of total incidence across treatment groups for the ATC level 1 (CM1 only) and in descending order of total incidence of ingredient within ATC level (CM1) or overall (CM8). In case of a tie, sort tied ingredients alphabetically.	SAC

CONFIDENTIAL

BRF116613

Table No.	Title	Population	Component / Therapeutic Area (hyperlinked to IDSL LN DB)	IDSL No. or Example Shell No.	Study-Specific Display Notes	Deliverable Priority
1.6010	Summary of Overall Compliance Based on Exposure	ITT	Compliance	COMP1		SAC

18.1.1.2. ICH Listings

Listing No.	Title	Population	Component / Therapeutic Area (hyperlinked to IDSL LN DB)	IDSL No. or Example Shell No.	Study-Specific Display Notes	Deliverable Priority
21.0010	Listing of Randomized [Planned] and Actual Treatments	ITT	Randomization Number/Core	TA1		SAC
21.0020	Listing of Subjects Excluded from Analysis Populations	ITT	Subject Accountability/Oncology	POP2		SAC
21.0030	Listing of Study Treatment Discontinuation Record	ITT	Investigational Product Discontinuation/Core	SD2		SAC
21.0040	Listing of Subjects with Inclusion/Exclusion Criteria Deviations	ITT	Inclusion & Exclusion Criteria/Core	IE3		SAC
21.0050	Listing of Protocol Deviations	ITT	Protocol Deviations/Core	DV2		SAC
21.0060	Listing of Demographic Characteristics	ITT	Demography/Core	DM2		SAC
21.0070	Listing of Race	ITT	Demography/Core	DM9		SAC
21.0800	Listing of Overall Compliance	ITT	Compliance	COMP2		SAC
21.0090	Listing of Drug Accountability	ITT	Compliance	COMP3C		SAC
21.0091	Listing of Randomized and Actual Treatments	ITT	Compliance	COMP2		SAC

18.1.1.3. Other Study Population Listings

Listing No.	Title	Population	Component / Therapeutic Area (hyperlinked to IDSL LN DB)	IDSL No. or Example Shell No.	Study-Specific Display Notes	Deliverable Priority
30.0010	Listing of Substance Use	ITT	Substance Use/Core	SU2		SAC
30.0020	Listing of Current Cancer Related Medical Conditions	ITT	Medical Conditions/Core	MH2	If conditions not coded, classification column will not be included on the listing.	SAC
30.0021	Listing of Past Cancer Related Medical Conditions	ITT	Medical Conditions/Core	MH2	If conditions not coded, classification column will not be included on the listing.	SAC
30.0022	Listing of Current Non-Cancer Related Medical Conditions	ITT	Medical Conditions/Core	MH2	If conditions not coded, classification column will not be included on the listing.	SAC
30.0023	Listing of Past Non-Cancer Related Medical Conditions	ITT	Medical Conditions/Core	MH2	If conditions not coded, classification column will not be included on the listing.	SAC
30.0030	Listing of Disease Characteristics at Initial Diagnosis	ITT	Disease Characteristics/Oncology	DC3	Should include time since initial diagnosis in weeks, stage at initial diagnosis, and date of initial diagnosis	SAC
30.0040	Listing of Disease Characteristics at Screening	ITT	Disease Characteristics/Oncology	DC4	Sections include: Measurable disease at baseline, Presence of non-target lesions at baseline, and Stage	SAC
30.0050	Listing of Metastatic Disease at Screening	ITT	Metastatic Disease/Oncology	MD2		SAC
30.0060	Listing of Prior Anti-Cancer Therapy	ITT	Anti-Cancer Therapy/Oncology	AC6		SAC
30.0070	Listing of Prior Anti-Cancer Radiotherapy	ITT	Anti-Cancer Therapy/Oncology	AC7		SAC
30.0080	Listing of Prior Cancer Related Surgical Procedures	ITT	Surgical-Medical Procedures/Oncology	OSP3		SAC
30.0081	Listing of Prior Non-Cancer Related Surgical Procedures	ITT	Surgical-Medical Procedures/Oncology	OSP3		SAC
30.0090	Listing of Post Treatment Anti-Cancer Therapy	ITT	Follow-up/Oncology	FAC3		SAC

CONFIDENTIAL

BRF116613

Listing No.	Title	Population	Component / Therapeutic Area (hyperlinked to IDSL LN DB)	IDSL No. or Example Shell No.	Study-Specific Display Notes	Deliverable Priority
30.0100	Listing of Concomitant Medications	ITT	Concomitant Medications/Core	CM2		SAC
30.0101	Listing of Blood or Blood Supportive Care Products while On-Therapy	ITT	Concomitant Medications/Core	CM2		SAC
30.0110	Relationship between ATC Level 1, Ingredient, and Verbatim Text for Anti-Cancer Therapy	ITT		See Mock-Up	Have Treatment information above columns. Column order is ATC Level 1, Ingredient, and Verbatim Text	SAC

